(Montreal Cognitive Assessment, Version 8.1), and RUDAS (Rowland Universal Dementia Scale). The cognitive screening questions will be administered to new study participants at Visit 1 after consenting. Previously enrolled participants will be offered the cognitive screening questions at their next visit (either Visit 2 or Visit 3). If a previously enrolled participant wants to complete the cognitive screening questions, they will be re-consented with the updated consent form and the cognitive screening questions will be administered at the visit when they are re-consented. If a previously enrolled participant does not want to participate in the cognitive screening questions, we will not re-consent them and they will complete the rest of the protocol as outlined in the original consent form, which contains all of the assessments in the table above with the exception of the cognitive screening questions.

Participants will be randomized into one of two testing schedule orders to receive the core battery for in-person testing. The core battery includes the following questionnaires: PROMIS Profile, PHQ-9, Berlin Questionnaire, Purpose and Meaning (NIH Toolbox), RRS, PTSD Checklist. The following table indicates the two orders for core battery testing:

Order 1	Order 2
PROMIS Profile	PHQ-9
Berlin Questionnaire	RRS
Purpose and Meaning (NIH Toolbox)	PTSD Checklist
PTSD Checklist	Purpose and Meaning (NIH Toolbox)
RRS	Berlin Questionnaire
PHQ-9	PROMIS Profile

Next, depending on which randomized condition, the participant will complete all the questionnaires via paper-and-pencil or using a talking-touchscreen format which is computerized and give the participant the opportunity to have questions read aloud.

At the end of each visit, a research assistant will briefly speak with the participant to learn about their experience during the visit and to find out if those randomized to the talking-touchscreen format utilized the audio files. To assess this, we will ask the following questions and record the responses on REDCap:

- 1. How did the questionnaires go?
- 2. Did you use the audio? (all, some, none)
- 3. On a scale of 0-10 (with 0 being very unhelpful and 10 being very helpful), how helpful did you find the audio? (1-10)

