Data on social and medical history (e.g., age, date of birth, gender, and race/ethnicity) will be obtained from the patient's electronic medical record to maintain privacy. Medical history data will be extracted from Epic via the EDW for purposes of calculating a single index of medical comorbidity, the Charlson Comorbidity Index. This index uses the presence versus absence of administrative codes in the medical record to determine certain diseases and syndromes that may be present; these include myocardial infarction, congestive heart failure, peripheral vascular disease or bypass, cerebrovascular disease or transient ischemic disease, hemiplegia, pulmonary disease/asthma, diabetes, diabetes with end organ damage, renal disease, mild liver disease, severe liver disease, gastric or peptic ulcer, cancer (lymphoma, leukemia, solid tumor), metastatic solid tumor, dementia or Alzheimer's disease, rheumatic or connective tissue disease, HIV or AIDS, hypertension, skin ulcers/cellulitis, depression, and warfarin use. These data will be combined into a single number that summarizes the degree of comorbidity faced by the individual patient. Data will be analyzed to determine whether health literacy and medical comorbidity interact in determining responses to questionnaires.

Other than the above-mentioned medical history and demographic variables, no other data will be retrieved from Epic.

Participants will interact with the study coordinator who will verify age, date of birth, race, and ethnicity date. The study coordinator will be the point person to answer any and all questions about the study. All study procedures will be conducted in a private space. Participants will be informed that they are allowed to skip any question that makes them feel uncomfortable or that they would not like to answer. Participants will be made aware of all of the examinations and research procedures that will take place ahead of time so that they are fully aware of what is required of them. The subject will be able to withdraw from the research study at any time. The research team is permitted to access the participants' medical records, which includes social and medical history. Only information that is pertinent to the research study will be viewed and collected. Any information that will be put into our databases will be collected from the EDW.

14.0 Confidentiality and Data Management:

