PROMIS Profile	To assess health-related quality of life.
PHQ-9	Self-report measure of depression.
Berlin Questionnaire (for sleep)	Self-report measure of sleep quality.
Purpose and Meaning (NIH Toolbox)	Self-report measure of the degree of meaning and purpose a person feels in their life.
RRS	Self-report measure of negative, repetitive thoughts.
PTSD Checklist	Self-report measure of posttraumatic stress disorder symptoms.
*C-SSRS Lifetime	Self-report measure of recent history of suicidal ideation and behavior. (This is not a variable of interest that will be used only to ensure patients' safety).
*C-SSRS Last Contact	Self-report measure of suicidal ideation and behavior since the individual's most recent assessment. (Used only as necessary to ensure patients' safety).
Exit Interview	

are estimated using full-information approaches that use all available data and can accommodate missing responses. We do not foresee a need for an imputation strategy, but if that were to become necessary, we will update this plan accordingly before running any analyses.

Study Design

This is a randomized experiment aimed at determining whether talking touchscreen technology can reduce DIF and provide a better testing experience, relative to paper-based testing. The original study design is shown below in Table 2, although as a result of the COVID-19 pandemic, we were unable to recruit all 1216 participants, but instead collected additional longitudinal data on a subset of participants ($n = 304$)

Table 2: Study Design			
Northwestern		BUMC	

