304 English speaking 152 with low health literacy 76 women g1 38 randomized to paper-based 19 Order 1 19 Order 2 38 randomized to talking touchscreen 19 Order 1 19 Order 2 76 men g2 38 randomized to paper-based 19 Order 1 19 Order 2 38 randomized to talking touchscreen 19 Order 1 19 Order 2 152 with adequate health literacy 76 women g3 38 randomized to paper-based 19 Order 1 19 Order 2 38 randomized talking touchscreen 19 Order 1 19 Order 2 76 men g4 38 randomized to paper-based 19 Order 1 19 Order 2 38 randomized talking touchscreen 19 Order 1 19 Order 2	304 Spanish speaking 152 with low health literacy 76 women g5 38 randomized to paper-based 19 Order 1 19 Order 2 38 randomized to talking touchscreen 19 Order 1 19 Order 2 76 men g6 38 randomized to paper-based 19 Order 1 19 Order 2 38 randomized to talking touchscreen 19 Order 1 19 Order 2 152 with adequate health literacy 76 women g7 38 randomized to paper-based 19 Order 1 19 Order 2 38 randomized talking touchscreen 19 Order 1 19 Order 2 76 men g8 38 randomized to paper-based 19 Order 1 19 Order 2 38 randomized talking touchscreen 19 Order 1 19 Order 2	304 English speaking 152 with low health literacy 76 women g9 38 randomized to paper-based 19 Order 1 19 Order 2 38 randomized to talking touchscreen 19 Order 1 19 Order 2 76 men g10 38 randomized to paper-based 19 Order 1 19 Order 2 38 randomized to talking touchscreen 19 Order 1 19 Order 2 152 with adequate health literacy 76 women g11 38 randomized to paper-based 19 Order 1 19 Order 2 38 randomized to talking touchscreen 19 Order 1 19 Order 2 76 men g12 38 randomized to paper-based 19 Order 1 19 Order 2 38 randomized to talking touchscreen 19 Order 1 19 Order 2	304 Spanish speaking 152 with low health literacy 76 women g13 38 randomized to paper-based 19 Order 1 19 Order 2 38 randomized to talking touchscreen 19 Order 1 19 Order 2 76 men g14 38 randomized to paper-based 19 Order 1 19 Order 2 38 randomized to talking touchscreen 19 Order 1 19 Order 2 152 with adequate health literacy 76 women g15 38 randomized to paper-based 19 Order 1 19 Order 2 38 randomized to talking touchscreen 19 Order 1 19 Order 2 76 men g16 38 randomized to paper-based 19 Order 1 19 Order 2 38 randomized to talking touchscreen 19 Order 1 19 Order 2

Study Timepoints

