Multiple regression analyses will be conducted using the *lm()* function in base R to test a moderation model for the PHQ-9 and PROMIS depression scale separately with health literacy (a continuous score from Health LiTT) acting as the proposed moderator between depression symptoms and pain intensity and interference, sleep disturbance, fatigue, and rumination. PROMIS profile scale scores will be entered into the regression model together. Health literacy will then be added as a moderator. In accord with our hypotheses, the addition of health literacy into the model should explain a significantly greater portion of the variance than symptom scores alone. PROMIS profile scale scores will then be removed from the model in a step-down procedure to determine the contribution of each scale to the model. We hypothesize that there will be a significant interaction between health literacy and symptoms scores. Specifically, we hypothesize that having higher health literacy will result in a stronger association between rumination and depression, whereas individuals with lower health literacy will evidence a stronger association between somatic symptoms (pain, fatigue, and sleep disturbance) and depression. Additionally, we predict that there will be a greater effect of health literacy for analyses involving the PHQ-9 than the PROMIS. We will also compare standardized beta coefficients to determine the strength of the effect for each variable. As we anticipate few instances of missing data due to our computerized administration, listwise deletion will be used in the presence of missing data.

Meaning and Purpose Analyses

DIF Analysis. In addition to the lordif approach described above, we will conduct DIF analysis using the moderated nonlinear factor analysis (MNLFA) approach, which allows health literacy to be continuous, rather than categorical (high versus low). Our analyses will examine the impact of health literacy on DIF as well as possible moderation by administration type (pencil-and-paper versus talking touchscreen). The MNLFA enables the examination of both variables simultaneously. Our a priori hypothesis is that DIF will be observed across levels of health literacy for paper-and-pencil based testing. We further hypothesize that DIF will also be found for the talking touchscreen, but for fewer items. Mplus permits IRT analyses with constraints imposed such that each item slope is linearly related to external variables – in our case, this would be:

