Demographic information was collected at the baseline interview. We collected data on age, sex/gender, race and ethnicity, primary language, and education level. The covariates/confounders assessed in our model include age, sex/gender, and education, chosen based on the conceptual model exploring the relationship between health literacy and various health outcomes.⁴⁹ We will report descriptive statistics of demographic variables. To ease interpretation, **Education** will be treated as a dichotomous variable with two categories: high school/GED level education or less versus more than high school education. **Gender** will be treated as dichotomous variable (male/female), because no participants identified as transgender or non-binary in this sample (although our assessment procedures were designed to accommodate non-binary participants). **Age** (in years) will be treated as continuous variable.

Primary Covariate

We will focus on race and ethnicity as primary covariate in our mediation analysis exploring the relationship between race/ethnic status and vaccine confidence. **Race/ethnicity status** will be dummy coded in the following way using white (non-Hispanic) as the reference category:

- X1 =1 if Black/African American (Non-Hispanic); X1=0 otherwise
- X2 = 1 if Latin X/Hispanic Ethnicity; X2=0 otherwise
- X3 = 1 if Other Race/Ethnicity (Non-white); X3 =0 otherwise

The other race category will include participants of mixed race and individuals who identified as Asian, Pacific Islander, or American Indian, categories with fewer participants.

Health literacy: Hypothesized Mediator

Health literacy was measured at baseline using Health Literacy Assessment Using Talking Touchscreen Technology (Health LiTT),⁵⁰ a computerized assessment that does not require an interviewer. This measure has been validated in English and Spanish. We will define **Health Literacy** as a continuous T score obtained from Health LiTT where a higher score is associated with greater degree of health literacy.

Vaccine Confidence Index: Outcome

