Mean centering. Because we plan to test interaction effects (i.e., moderation), we will mean-center brooding, reflection, PROMIS depression, age, and Health LITT. If any additional continuous covariates are used in exploratory analyses, these will also be centered around the mean.

Exploratory Structural Equation Modelling

All items in the cognition measures (as latent variables) and brooding and reflection (as scores) will be included (see above). Based on the parallel analysis to determine the number of factors, multiple exploratory factors from

the cognitive measures will be regressed on our two covariates of interest – brooding and reflection. We anticipate that brooding and reflection will be inversely related with cognition, in particular items related to memory and executive function. In other words, higher levels of rumination will be associated with lower levels of cognition.

We will conduct these analyses using Mplus. We will report all fit indices, unstandardized associations among variables, corresponding SEs, and significance tests at a Type I error rate of .05.

Scoring rumination

Rumination will be measured using the Ruminative Responses Scale (RRS) short form, a 10-item form that includes two subscales, brooding and reflection. The RRS uses a four-point response scale for each item with a total score derived from the sum of the individual items. Higher scores indicate higher levels of rumination. All variables will be examined in a continuous manner, rather than using cut scores. If 80% or more of the items are present, we will score the subscale using prorating.

Hypotheses and testable predictions

We hypothesize that rumination will have a significant association with cognition. Specifically, higher scores in both domains of rumination (brooding and reflection) will be related to lower scores on cognitive factors. Overall, we expect cognition to be more strongly related to brooding than reflection. In past work ([name] & Raes, 2014), we found that the brooding factor was more robust than the reflection factor. Thus, it is possible that the more reliable brooding scale will have larger associations with cognition. However, the literature contains mixed findings with regard to the relative contributions of brooding versus reflection (e.g.,^{57, 58}).

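### Listwise deletion in the depression moderation models is justified by computerised administration, but half of the planned sample was randomised to paper and no partial-scale scoring rule is given

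*SAP*

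**What the plan says.** The SAP section on prediction of depression fits multiple regressions with lm(), one set for the PHQ-9 and one for PROMIS depression. Continuous Health LiTT moderates the effects of pain, sleep disturbance, fatigue and rumination. The PHQ-9 is described as a 0–27 score from nine items and the RRS as a sum over ten items. The missing-data rule is: "As we anticipate few instances of missing data due to our computerized administration, listwise deletion will be used in the presence of missing data". The section is not restricted to touchscreen users.

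The mode of administration is set elsewhere:

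- Protocol 4.3: by randomised condition, "the participant will complete all the questionnaires via paper-and-pencil or using a talking-touchscreen format". It adds: "The core battery includes the following questionnaires: PROMIS Profile, PHQ-9, Berlin Questionnaire, Purpose and Meaning (NIH Toolbox), RRS, PTSD Checklist".
- SAP Table 2 repeats the same split in every stratum: "38 randomized to paper-based 19 Order 1 19 Order 2 38 randomized to talking touchscreen".
- The vaccine-confidence addendum of the SAP describes Health LiTT as "a computerized assessment that does not require an interviewer".

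On missing answers, Protocol 13.0 states: "Participants will be informed that they are allowed to skip any question that makes them feel uncomfortable". SAP Study Objectives reports 728 participants with a health literacy assessment and says that some lack later questionnaire data. SAP Missing data promises item-level missingness tables, subgroup checks by literacy, site and mode as needed, and an update of the plan if imputation proves necessary. It uses full-information estimation for the DIF models. A partial-scale rule appears only in the later rumination plan, under Scoring rumination: "If 80% or more of the items are present, we will score the subscale using prorating".

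**The concern.** Computerised administration can be offered as a reason to expect few skipped items only for people who answer on a computer. In these models, every variable except the moderator comes from the battery whose mode was randomised, so the reason covers about half of the planned data.

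Three things are at stake.

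- **Precision.** With summed scores and no partial-scale rule, one skipped PHQ-9 or RRS item can remove a participant from the model.
- **Bias, under a condition.** If skipping depends on depression given the covariates, complete-case coefficients can be biased. This is possible here, because the outcome is itself a set of sensitive questions that participants may decline.
- **Comparability.** The SAP predicts a larger literacy effect for the PHQ-9 than for PROMIS depression, and it removes scales in a step-down procedure. Under case deletion in lm(), the two outcome models can use different people, and removing a scale can bring dropped cases back. No common analysis set is defined.

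**Working it through.** **1. Share of the design on paper.** Table 2 has 16 strata, each with 38 paper and 38 touchscreen participants. 16 × (38 + 38) = 1216, which reproduces the planned total that the SAP says it fell short of ("we were unable to recruit all 1216 participants"). Paper: 16 × 38 = 608, and 608 / 1216 = 50%. The split among the achieved 728 is not reported; at 1:1 it would be 364 on paper.

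**2. Loss from sum-scored items.** The documents give no skip rate p, so it is assumed. With independent skips and no prorating, the share with at least one missing item among k items is 1 − (1 − p)^k. The PHQ-9 model has k = 9 + 10 = 19 (PHQ-9 plus RRS). The PROMIS-depression model has k = 10 (RRS only). For the last column, one missing item is allowed on the PHQ-9 (8/9 = 89%; 7/9 = 78% fails) and one on each RRS subscale (4/5 = 80%, assuming five items each). The loss is then 1 − P(at most 1 of 9 missing) × P(at most 1 of 5 missing)².

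| Skip rate per item | PHQ-9 model, k = 19 | PROMIS-depression model, k = 10 | PHQ-9 model with 80% prorating |
|---|---|---|---|
| 0.25% | 4.6% | 2.5% | 0.03% |
| 0.5% | 9.1% | 4.9% | 0.1% |
| 1% | 17.4% | 9.6% | 0.5% |
| 2% | 31.9% | 18.3% | 2.1% |

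These are losses among people who skip at that rate. If only paper participants skipped and the split were 1:1, the loss over the whole PHQ-9 model would be half: about 2.3% to 16%.

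**3. Selectivity.** Assume 728 / 4 = 182 people in each mode-by-literacy cell. Suppose incomplete rates are 5% (paper, low literacy), 2% (paper, adequate) and 1% (touchscreen). About 16 people are lost, and low-literacy participants make up 49.6% of those retained. With rates of 30%, 10% and 2%, about 80 are lost, and that share is 47.2%.

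**4. Bias.** A simulation with N = 728 and 3,000 replicates used one symptom score, a true interaction of 0.10, 1:1 mode, 1% incomplete on touchscreen and most of the loss on paper.

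| Paper missingness depends on | Cases lost | Mean interaction, complete cases | SD of estimate, all data → complete cases |
|---|---|---|---|
| Literacy only | 8.3% | 0.100 | 0.031 → 0.033 |
| Literacy and depression | 7.3% | 0.101 | 0.031 → 0.032 |
| Literacy, depression and their product | 7.8% | 0.106 | 0.031 → 0.033 |

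The largest shift, 0.1058 − 0.100 = 0.0058, is about 0.18 of the standard error (0.0058 / 0.033). These scenarios are assumed and do not bound the bias.

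**The case against.** A fair defence has five parts.

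- **Scoring versus case rules.** A reader might infer that the SAP gives the RRS two contradictory missing-data rules. It does not strictly do so. The 80% rule says how to form a score, and listwise deletion says what to do when a score is absent; one can prorate first and delete afterwards. The data-quality section also refers to existing scoring rules that the SAP does not reproduce. What stands is that the moderation section describes plain sums and states no partial-scale rule.
- **Bias.** A reader might infer that dropping low-literacy participants biases the interaction. If missingness depends only on Health LiTT or other model covariates and the model is correct, complete-case coefficients stay unbiased and only precision suffers. This objection stands.
- **Magnitude.** The skip rates are assumed. Skips clustered within people lose fewer cases at the same item rate, and permission to skip applies in both modes, so it is not evidence of selective loss on paper. This also stands.
- **Existing safeguards.** The missing-data section plans to examine missingness by literacy and mode. That helps, but it is conditional, not tied to these models, and does not override the deletion rule.
- **Timing.** The version notes of the rumination plan (June 2021) say that some analyses from this section had already been run. Replacing the main estimator now would be a change after results were available. This argues for adding an analysis beside the stated one.

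**Conclusion.** The stated reason for listwise deletion is wrong for half of the planned design, on the forms that supply both outcomes and all symptom predictors. As written, the section can lose precision, can let compared models rest on different participants, and can introduce some bias if skipping depends on depression given the covariates.

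The size is unknown. The ranges of 4.6% to 32% (PHQ-9 model) and 2.5% to 18% (PROMIS-depression model) rest on assumed skip rates of 0.25% to 2%, independent skips and no prorating. Bias was small in the scenarios tried.

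The documents do not support the stronger reading that low-literacy or paper participants are in fact being lost selectively, because no rate or pattern of missingness is reported. Nor does the point reach the DIF analyses that compare paper with touchscreen, since those use full-information estimation.

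**What to change.** In the SAP section on prediction of depression:

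1. Remove the computerised-administration rationale.
2. Apply the 80% prorating rule from Scoring rumination to the RRS and the PHQ-9. At the skip rates in the table, this recovers nearly all cases lost to single skipped items.
3. Define a common analysis set for the PHQ-9 versus PROMIS-depression comparison and for the nested step-down models.
4. Report complete-case rates by mode and by Health LiTT level.
5. Add a multiple-imputation sensitivity analysis, reported beside the complete-case result. The imputation model should include the outcome, mode, Health LiTT and the Health LiTT-by-symptom product terms; leaving out the products can attenuate the interaction under test.

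Because some of these analyses have already been run, record all of this as a justified change, as the SAP's statistical overview requires. The cost is slightly more programming, a documented post-hoc change, and the exclusion from the common-set comparisons of people who lack one of the scores.
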